5.2.6. Subgroup Analysis

For each of the subgroups defined in Section 2.5, the proportion of subjects achieving an IGA score of 0/1 and a PASI 75 response at Week 16 by treatment group will be summarized. Differences in the proportion and the associated exact 95% confidence intervals (CI) for the differences will be provided.

In addition, the proportion of subjects achieving an IGA score of 0/1 and the proportion of PASI 75 responders at Week 16 by region, country and investigator site will be summarized.

5.2.7. Per Protocol Analyses

Per protocol analyses will be performed for the co-primary endpoints, similar to the primary analyses but based on the per protocol analysis set as defined in Section 2.4.1.2.

5.3. Major Secondary Endpoints

The analyses for the major secondary endpoints will be performed in the order listed in Section 5.1.1.1.

The sections below outline the major secondary analyses to be performed, as well as the analysis methods and the data imputation rules.

5.3.1. Definition

There are 4 major secondary endpoints in this study to be compared between the guselkumab group and the placebo group:

- The proportion of participants achieving a PASI 90 response at Week 16.
- The proportion of participants achieving an IGA score of cleared (0) at Week 16.
- The proportion of participants achieving a PASI 100 response at Week 16.
- The change from baseline in CDLQI at Week 16.

5.3.2. Major Secondary Estimands

5.3.2.1. Estimands for Binary Endpoints of IGA or PASI Responses

Population: subjects with chronic plaque psoriasis who are randomized to guselkumab or placebo in Part 1 of the study.

Variable: the endpoint is defined as the proportion of subjects who achieve a PASI 90 response at Week 16, the proportion of subjects who achieve an IGA score of cleared (0) at Week 16, or the proportion of subjects who achieve a PASI 100 response at Week 16. Non-responder status is assigned after a subject meets TF or rescue treatment criteria.

Intercurrent Events: the intercurrent event is captured through the variable definition.

Population-level summary: difference in response proportions between guselkumab group and placebo group.

5.3.2.2. Estimands for Continuous Endpoint of CDLQI

5.3.2.2.1. Composite Strategy

The composite strategy assesses the treatment effects not only based on the variable measurements, but also based on intercurrent events defined in TF and rescue treatment criteria.

Population: subjects with chronic plaque psoriasis who are randomized to guselkumab or placebo in Part 1 of the study.

Variable: the endpoint is defined as the change from baseline in CDLQI at Week 16. Zero change is assigned after a subject meet TF or rescue treatment criteria.

Intercurrent Events: the intercurrent event is captured through the variable definition.

Population-level summary: difference in LSmean between guselkumab group and placebo group.

5.3.2.2.2. Treatment Policy Strategy

The treatment policy strategy is to use all observed data collected for the endpoint, regardless of the occurrence of the intercurrent event (i.e. TF or rescue treatment).

Population: subjects with chronic plaque psoriasis who are randomized to guselkumab or placebo in Part 1 of the study.

Variable: the endpoint is defined as the change from baseline in CDLQI at Week 16.

Intercurrent Events: regardless of the intercurrent event of meeting TF or rescue treatment criteria.

Population-level summary: difference in LSmean between guselkumab group and placebo group.

5.3.3. Analysis Methods

For categorical response parameters (PASI 90, IGA score of 0, PASI 100 response) at Week 16, the Fisher's exact test, stratified by age group and region, will be used to compare the proportion of participants responding to treatment between the guselkumab and placebo group. The p-values and the differences in proportions with exact 95% confidence intervals will be presented.

The change from baseline in CDLQI at Week 16 will be analyzed using a Mixed Model for Repeated Measures (MMRM) model to test the difference between treatment groups and adjust for missing data. The independent variables for this model may include treatment group (guselkumab, placebo, and etanercept), region (NA, EU), age group (6 - <12 years, 12- <18 years), baseline CDLQI score, visit week, an interaction of baseline CDLQI score and visit, and an interaction of treatment and visit as appropriate. An unstructured (UN) variance-covariance matrix for repeated measures within a subject will be used. The treatment difference between guselkumab and the placebo group will be estimated by difference in LSmeans. The 95% CIs for difference in LSmean between the groups and p-values will be calculated.

In addition, the comparison between etanercept and placebo for the major secondary endpoints will be performed and nominal p-values will be reported.

5.3.4. Data Handling

Data handling rules specified in Section 5.2.4 will be applied to the major secondary analyses. After applying the treatment failure or rescue treatment rules, the remaining missing data will be imputed. Zero will be assigned to change from baseline in CDLQI score, and non-responder status will be assigned to PASI 90, IGA 0/1, and PASI100 response variables.

5.3.5. Sensitivity Analysis

To assess the robustness of the major secondary endpoint analysis results, sensitivity analyses will be conducted as specified in .Table 4

Endpoint	Estimand	Methods
The proportion of subjects who achieve a PASI 90 response at Week 16	Sensitivity analysis 1	Observed data after apply TF and rescue treatment rule
	Sensitivity analysis 2	Multiple imputation with FCS logistic regression (similar to the sensitivity analysis for the primary endpoint with the same seed and the number of imputations)

The proportion of subjects who achieve an IGA score of cleared (0) at Week 16	Sensitivity analysis 1	Observed data after apply TF and rescue treatment rule
	Sensitivity analysis 2	Multiple imputation with FCS logistic regression (similar to the sensitivity analysis for the primary endpoint with the same seed and the number of imputations)
The proportion of subjects who achieve a PASI 100 response at Week 16	Sensitivity analysis 1	Observed data after apply TF and rescue treatment rule
	Sensitivity analysis 2	Multiple imputation with FCS logistic regression (similar to the sensitivity analysis for the primary endpoint with the same seed and the number of imputations)
The change from baseline in CDLQI at Week 16	Sensitivity analysis 1	After apply TF and rescue treatment rule, multiple imputation with Markov Chain Monte Carlo (MCMC) algorithm will be used, which assumes that all the variables in the imputation model have a joint multivariate normal distribution
	Supplementary analysis	MMRM model will be used to test the difference between treatment groups based on observed data. No TF or rescue treatment rule apply.

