5.1.3.6. Missing Data Imputation

After the treatment failures and rescue treatment rules are applied, the remaining missing data will be handled as follows for all of the efficacy analyses including the analyses at key visits (eg Week 16) and over time through Week 52:

- Non-responder imputation will be applied for binary efficacy endpoints.
- No imputation will be performed for missing post baseline continuous values. The statistical model (ie, MMRM) will adjust for missing data.

For the analyses related to the time to event endpoints during the withdrawal and retreatment period, missing PASI score after the Week 16 visit will not be imputed and the value will remain as missing after applying treatment failure rules.

For the efficacy analyses that evaluate the efficacy of retreatment or initiation of guselkumab, after the treatment failure rules are applied, no imputation will be performed for missing data following the retreatment or initiation of guselkumab.

For the efficacy analyses through LTE period, no treatment failures and no missing data imputation will be performed, and the analyses will be based on observed data.

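### Every CDLQI analysis in SAP Table 4 takes residual missing data as missing at random, so none tests informative missingness; SAP 5.1.3.6 and 5.3.4 also disagree on the main analysis

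*SAP*

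**What the plan says.** - **Main model, SAP 5.3.3.** CDLQI change "will be analyzed using a Mixed Model for Repeated Measures (MMRM) model to test the difference between treatment groups and adjust for missing data". On the covariance: "An unstructured (UN) variance-covariance matrix for repeated measures within a subject will be used".
- **General missing-data rule, SAP 5.1.3.6.** After the treatment-failure and rescue rules: "No imputation will be performed for missing post baseline continuous values. The statistical model (ie, MMRM) will adjust for missing data".
- **Rule for the major secondary endpoints, SAP 5.3.4.** "After applying the treatment failure or rescue treatment rules, the remaining missing data will be imputed", followed by "Zero will be assigned to change from baseline in CDLQI score".
- **Sensitivity analysis, SAP 5.3.5, Table 4.** The CDLQI row keeps the treatment-failure and rescue rules and then says "multiple imputation with Markov Chain Monte Carlo (MCMC) algorithm will be used". The assumption it states is joint normality of the imputation variables. It gives no imputation variables, seed, number of imputations or post-imputation model. The binary rows carry the seed and number over from 5.2.5.
- **Supplementary analysis, same table.** An MMRM on observed data without the treatment-failure and rescue rules. It matches the treatment policy strategy of 5.3.2.2.2.
- **Place in the testing.** CDLQI is the last endpoint in the fixed sequence, both globally (5.1.1.1) and for the US-FDA set (5.4.1).

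**The concern.** SAP 5.3.5 says its analyses are there to assess robustness. For missing CDLQI values, the assumption that cannot be checked from the data is that people with a missing Week 16 score would have done as well as similar people in their own arm who were observed. A sensitivity analysis is useful if it relaxes that assumption. Neither CDLQI row in Table 4 does.

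If the main analysis is the MMRM without imputation, the MCMC analysis makes the same two assumptions (missing at random, joint normality) on the same two post-baseline visits, Weeks 8 and 16. The two results would agree because they share a model. That agreement could be reported as robustness of an alpha-controlled result when robustness had not been tested. If the main analysis is the zero-change rule of 5.3.4, the comparison does mean something, but it sets one fixed value against missing at random and explores nothing in between or beyond.

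**Working it through.** **Inputs from the documents.** About 40 guselkumab and 25 placebo participants (SAP 1.4). CDLQI after baseline at Weeks 8 and 16 (protocol 1.3.1; SAP 5.5.2.1.3.1). Two-sided 5% level. The documents state no CDLQI effect, SD, missingness rate or power, so there is no figure of the plan's own to reproduce.

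**Assumptions, not in the documents.** Week 16 difference -5 points; residual SD 5; visit correlation 0.6; baseline mean 9, SD 6; dropout after Week 8 with probability 5%, 10% or 20% at an average outcome, rising with worse outcome. Etanercept, age group and region were left out. There were 600 simulated trials per scenario and 50 imputations each.

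**Estimators of the Week 16 difference.**
1. *MMRM* (factored normal likelihood, terms by visit): b16 + g x b8. Here b8 is the treatment effect at Week 8. b16 and g are the coefficients of treatment and of the Week 8 value in the Week 16 regression among those observed.
2. *Normal-model MI, treatment included*: draw missing Week 16 values from the regression on treatment, baseline and Week 8, then fit ANCOVA.
3. *Normal-model MI, treatment omitted* from the imputation regression.
4. *Zero change* for missing values, as in 5.3.4, then ANCOVA.

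| Dropout depends on | Level | Full data | MMRM | MI, treatment in | MI, treatment out | Zero change | Mean gap, MI (treatment in) to MMRM |
|---|---|---|---|---|---|---|---|
| Week 8 value (missing at random) | 5% | -5.02 | -5.03 | -5.04 | -4.81 | -4.62 | 0.037 |
| | 10% | -5.02 | -5.00 | -5.00 | -4.60 | -4.29 | 0.049 |
| | 20% | -5.08 | -5.03 | -5.03 | -4.37 | -3.74 | 0.074 |
| Week 16 value, both arms | 5% | -5.03 | -5.02 | -5.02 | -4.79 | -4.61 | 0.035 |
| | 10% | -5.00 | -5.01 | -5.01 | -4.60 | -4.27 | 0.045 |
| | 20% | -5.02 | -5.01 | -5.01 | -4.29 | -3.72 | 0.067 |
| Week 16 value, guselkumab only | 5% | -5.00 | -5.32 | -5.32 | -5.18 | -4.83 | 0.022 |
| | 10% | -5.03 | -5.52 | -5.52 | -5.26 | -4.62 | 0.032 |
| | 20% | -5.00 | -5.81 | -5.81 | -5.30 | -4.13 | 0.044 |

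**If 5.1.3.6 governs.** With treatment in the imputation model, MI and MMRM differ by 0.02 to 0.07 points on average. Under guselkumab-only informative dropout both are off by the same amount: 5.32 - 5.00 = 0.32, 5.52 - 5.03 = 0.49, 5.81 - 5.00 = 0.81. When dropout is informative in both arms alike, the bias is near zero.

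**If 5.3.4 governs.** MI with treatment differs from zero change by 0.41 (5.02 - 4.61) to 1.29 (5.03 - 3.74) in the first two blocks, and by 0.49, 0.90 and 1.68 in the third.

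**If treatment is left out of the imputation model.** MI moves from the MMRM by 0.14 (5.32 - 5.18) to 0.72 (5.01 - 4.29).

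**What sets the size of a bias.** To a first approximation it is p x d. Here p is the proportion of guselkumab Week 16 values that are missing, and d is how much worse those participants truly are than missing at random predicts. With d = 6, p = 8% gives 0.48 and p = 15% gives 0.90.

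**Would significance change?** Full-data SE = 5 x sqrt(1/40 + 1/25) = 1.27, so the result stays significant while the effect exceeds 1.96 x 1.27 = 2.50. For an assumed effect of 5, the slack is 2.50, and d must reach 2.50/0.15 = 16.7 points at 15% missing. At 8% missing it must reach 31 points, beyond the 30-point scale. For an assumed effect of 3, the slack is 0.50, and d need only reach 3.3 points at 15% missing or 6.3 at 8%.

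**The case against.** The strongest objection is SAP 5.3.4. It is the section written for these endpoints, it sits between the main model and Table 4, and it gives residual missing CDLQI values zero change. On that reading the main analysis is not a missing-at-random analysis, and MCMC is a genuine contrast. This stands as a reading. Three things point the other way: an MMRM has little left to adjust for once every gap is filled; the composite strategy in 5.3.2.2.1 gives zero only after treatment failure or rescue; and 5.3.4 names IGA 0/1, which is not a major secondary endpoint in 5.3.1. The text does not settle it.

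Second, the exposed data are limited. Stopping for lack of efficacy or worsening psoriasis, and starting prohibited therapy, count as treatment failure (5.1.3.2), and rescue is handled likewise (5.1.3.5). All get zero change, and the MCMC analysis keeps that. Participants who stop drug but stay in the study return for at least 12 weeks after the last dose (protocol 7.1), so someone last dosed at Week 4 is followed to Week 16. This stands. What remains is study withdrawal, loss to follow-up, missed visits (including COVID-19 disruption) and questionnaires with two or more blanks.

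Third, the bias figures follow from assumed missingness and assumed loss of benefit, and CDLQI is last in both sequences, so no later test depends on it. Both parts stand.

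A reader might infer that MCMC is bound to reproduce the main result and should be dropped. The documents do not support that. Section 5.3.4 may govern, the imputation variables are not listed, and under 5.3.4 dropping MCMC would remove the only missing-at-random analysis of the composite estimand.

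**Conclusion.** The point holds in limited form. Table 4 contains no CDLQI analysis that departs from missing at random. If 5.1.3.6 and 5.3.3 govern, and treatment is in the imputation model, the MCMC analysis is expected to match the MMRM to within a few hundredths of a point and to share any bias, so agreement says nothing about informative missingness. If 5.3.4 governs, MCMC differs from the main analysis by about 0.4 to 1.7 points on the assumptions used, but no range of departures is examined. The conflict between the two sections leaves the main analysis undefined.

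A reader might also infer that the CDLQI effect will be overstated. The documents give no effect, SD or missingness to support that, and the simulation shows bias only when informative dropout differs between arms. Whether a departure could matter depends on the observed effect and the number of missing values. That is what a tipping-point analysis would report. This is a cheap improvement to the plan and does not put the endpoint in doubt.

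**What to change.** 1. Reconcile SAP 5.1.3.6 and 5.3.4 so that a single rule for residual missing CDLQI values defines the main analysis.
2. Keep the MCMC analysis in Table 4. State that the imputation model contains treatment, baseline CDLQI, age group, region and the Week 8 value. State the post-imputation model, and fix the seed and number of imputations as in 5.2.5.
3. Add to the CDLQI row a delta-adjusted tipping-point analysis on missing Week 16 values in the guselkumab arm, a placebo-reference (jump to reference) multiple imputation, or both. Either is informative whichever rule is chosen in step 1.

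The cost is SAP wording, a little standard programming, and a sensitivity estimate that may look slightly less favourable.

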5.4. US-FDA specific Primary and Major Secondary Efficacy Analyses

5.4.1. Multiplicity Adjustment for Testing Procedures

The US-FDA specific co-primary endpoints are:

- The proportion of subjects who achieve an IGA score of cleared (0) or minimal (1) at Week 16
- The proportion of subjects who achieve a PASI 90 response at Week 16

Both of the US-FDA specific co-primary endpoint analyses will be compared between the guselkumab treatment group and the placebo group and tested at a 2-sided α -level of 0.05. If one of the comparisons is not significant at the 2-sided α -level of 0.05, the co-primary endpoints will be considered not significant.

In addition, the following US-FDA specific major secondary endpoints will be compared between the guselkumab group and the placebo group:

- The proportion of subjects who achieve a PASI 75 response at Week 16.
- The proportion of subjects who achieve an IGA score of cleared (0) at Week 16.
- The proportion of subjects who achieve a PASI 100 response at Week 16.
- The change from baseline in CDLQI at Week 16

In order to control the overall Type 1 error rate, the US-FDA specific co-primary analyses and major secondary analyses will be tested in a fixed sequence as ordered above. That is, the analyses

of the major secondary endpoints will be performed only if both primary analyses are significant and will be performed in the fixed sequence testing approach, as specified above. If a given comparison between the guselkumab treatment group and the placebo group is not significant at the 2-sided α -level of 0.05, the remaining treatment group comparisons in this sequence will be considered not significant and will be considered as supportive analyses.

5.4.2. Analysis Methods

For US-FDA specific primary and major secondary endpoints, the proportion of participants responding to treatment will be compared between the guselkumab and placebo group in the same manner as the global primary and major secondary endpoints. Table 5 presents the differences between the US-FDA specific primary and major secondary endpoints to the global endpoints. The same endpoints are not listed.

Table 5: Differences between US-FDA specific primary and major secondary endpoints to global endpoints		
	Global endpoints	US-FDA specified endpoints
Co-primary	PASI 75 response at Week 16 is one of the co-primary endpoints.	PASI 90 response at Week 16 is one of the co-primary endpoints.
Major secondary	PASI 90 response at Week 16 is the first major secondary endpoint.	PASI 75 response at Week 16 is the first major secondary endpoint.
Analysis methods	Fisher's exact test, stratified by age group and pooled region, will be used to compare the PASI 90 and PASI 75 response rates between treatment groups.	Same
Sensitivity analyses	
 Observed data after apply TF and rescue treatment rule. Multiple imputation with FCS logistic regression. 	Same

5.5. Other Efficacy Variables)

Other secondary efficacy endpoints include

- Investigator's Global Assessment (IGA)
- Psoriasis Area and Severity Index (PASI)
- Percent of body surface area with psoriasis skin involvement (BSA)
- Children's Dermatology Life Quality Index (CDLQI)
- Family Dermatology Life Quality Index (FDLQI)

5.5.1. Definition

Refer to Section 0 for the definitions of the other efficacy endpoints described in the following section.

5.5.2. Analysis Methods

5.5.2.1. Secondary Analyses for Participants Randomized in Part 1

For Part 1, the other secondary efficacy analyses described in this section below will be based on the full analysis set combining subjects from Part 1a and Part 1b. All statistical testing will be performed at the 2-sided 0.05 significance level. Nominal p-values will be presented. The Fisher's exact test, stratified by age and region, will be used to compare the proportion of participants responding to treatment. Continuous response parameters will be compared using an MMRM analysis with fixed factors of treatment, baseline value, age, region, visit, treatment by visit and baseline by visit interaction terms. Life table estimates will be provided for the time to event variables. Subjects who meet loss of response criteria (eg, loss of PASI 90 response, loss of 50% Week 16 PASI improvement) will be considered an 'Event'. Subjects who did not meet the criteria for loss of response at Week 52 will be censored.

In addition, for the analyses related to patient reported outcomes (CDLQI and FDLQI), only subjects with baseline measurements will be included.

The analyses of other secondary efficacy analyses outlined in the following sections in general will be carried out for 2 periods.

Analyses through Week 16 (placebo controlled period)

Efficacy analyses at Week 16 and over time through Week 16 will be summarized by randomized treatment group at Week 0

- **Placebo:** subjects randomized to placebo group at Week 0
- **Guselkumab:** subjects randomized to guselkumab treatment group at Week 0
- **Etanercept:** subjects randomized to etanercept treatment group at Week 0

Analyses from Week 16 to Week 52 (withdrawal and retreatment period)

- Efficacy of PASI 90 responders at Week 16
 - After withdrawal of guselkumab: To evaluate the loss of response after withdrawal of study agent, efficacy analyses will be performed for subjects who were randomized to guselkumab at Week 0, were PASI 90 responders at Week 16 and were withdrawn from study agent after Week 16. Non-responder status will be assigned after retreatment for binary endpoints. The measurement at the time of retreatment will be carried forward after retreatment for continuous endpoints.
 - After retreatment with guselkumab: To evaluate the efficacy of retreatment with guselkumab, efficacy data at and after retreatment (ie, at the time of retreatment, 4 weeks after retreatment, 8 weeks after retreatment) will be summarized for subjects who were randomized to guselkumab at Week 0, were withdrawn from study agent

- at Week 16, experienced a loss of 50% of the Week 16 PASI improvement, and were retreated with guselkumab.
- For subjects who were randomized to placebo at Week 0, and were PASI 90 responders at Week 16, efficacy data will be listed after Week 16.
 - Efficacy of PASI 90 non-responders at Week 16
 - Efficacy analyses for those subjects who were PASI 90 non-responders at Week 16 will be performed for the following treatment groups.
 - ◆ **Placebo → Guselkumab:** Subjects who were randomized to placebo at Week 0, were PASI 90 non-responders at Week 16 and crossed over to guselkumab at Week 16.
 - ◆ **Guselkumab:** Subjects who were randomized to guselkumab at Week 0, were PASI 90 non-responders at Week 16 and continued to receive guselkumab at Week 16.
 - Efficacy of etanercept cross over subjects
 - ◆ **Etanercept → Guselkumab:** To evaluate the efficacy of guselkumab in subjects previously treated with etanercept, efficacy analyses will be performed from Week 20 through Week 52 for subjects who were randomized to etanercept at Week 0, and crossed over to guselkumab at Week 20.

